1. INTRODUCTION

This Statistical Analysis Plan (SAP) describes the planned analysis and reporting for the 28431754HFA3002 (**Canagliflozin: Impact on Health Status, Quality of Life, and Functional Status in Heart Failure – CHIEF-HF**) study. This Phase 3b study is being conducted in the United States (US) in participants with symptomatic HF stratified by HF (reduced ejection fraction [HFrEF] or preserved ejection fraction [HFpEF]) and compares the effectiveness of canagliflozin 100 mg versus placebo for improvement in HF symptoms measured by the Kansas City Cardiomyopathy Questionnaire - Total Symptom Score (KCCQ-TSS) (see [Appendix 1: The Kansas City Cardiomyopathy Questionnaire \(KCCQ\)](#)) after 12 weeks. This document contains details of the relevant definitions, data handling conventions and methods for analyses. The document will be finalized prior to database lock.

This SAP is based on the clinical study protocol (finalized first on 7 November, and subsequently amended on 7 February 2020 (Protocol **28431754HFA3002 Amendment 1**, dated **07 February 2020 - EDMS-ERI-154820237, version 3.0**) by Janssen Scientific Affairs, LLC) that provides details on the conduct of this study and operational aspects of clinical assessments and timing for completing a participant in this study.

Based on the last protocol amendment, changes were made to this SAP on December 30, 2020 and are listed on the preceding amendment page in this document. A final version of this SAP with editorial changes is posted on 1 July 2021.

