After approximately 10 months, the planned enrollment in this study is not expected to reach the target of 1900 participants by the scheduled end of study enrollment window in the first quarter of 2021. Instead, the final anticipated enrollment may only be in the range of about 400-480 participants. Consequently, a reduction in total sample size of this magnitude will have impact on the statistical power for the assumed effect size as well as for various other plausible effect sizes, shown by the figures below. At 50% statistical power, an effect size of 3.5 points in the KCCQ change score (assuming standard deviation is 18) can be detected with a minimum sample size of 400. For power $\geq 80\%$, the required sample size has to be at least 445 if the expected mean difference in KCCQ-TSS change score over 12 weeks is as high as 4.8, assuming the pooled standard deviation is 18. An effect size of this magnitude for the KCCQ-TSS change score was reported in the recently concluded DEFINE-HF study¹⁷. Robust improvements over baseline were also reported for additional KCCQ domains in this study as well as in the SOLOIST study^{17,18}.

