2.3.4. Safety Analysis Set

The safety analysis set includes all randomized participants who received at least 1 dose of study intervention. Summary of available safety data from all sources (claims and patient reported) will be based on this analysis set.

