6. SAFETY

Summaries of safety data will be based on the safety analysis set and will use claims data.

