For the prohibited medications, analysis period will include data from the date of informed consent until the end of double-blind treatment period. For all other concomitant medications, analysis period will include data from the date of informed consent until the end of the study. For the HRU data analysis, information collected from date of informed consent until the end of study will be considered in the final analysis.

For both the double-blind treatment period + 30 days after last dose and the 9-month entire study period, descriptive summaries (numbers and percentages) of participants having an SAE/AE of interest will be produced, including by participant's diabetes status (T2DM and non-T2DM) and by randomized intervention group. Discontinuations (and reported reasons) will be summarized by randomized intervention group based on available claims data.

There will be no reconciliation/analysis of SAE/AE data that are self-reported to the Call Center with the data obtained from the claims database.

A listing will be presented for treatment emergent hospitalizations and deaths for each randomized intervention group. AEs occurring between informed consent and the day prior to the first dose of study intervention will also be listed. This listing will be based on participants with informed consent into the study. Depending on the claims/pharmacy data, AEs occurring in participants who used prohibited (commercially available SGLT2is other than the study intervention, canagliflozin) will also be listed.

Based on pharmacy profiles of the participants after-consent in this study, the total number of participants concomitantly receiving UGT inducers during the double-blind treatment period will be summarized combined across both study intervention groups. If the number of such participants is >2% of the total 1,900 targeted for enrollment in this study, the users and non-users of UGT inducers will be summarized by each study intervention group as well and examined further (as

necessary) for any relationship to key study outcomes (eg, PRO endpoints and clinical outcomes reported in claims).

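### The UGT-inducer trigger in SAP 6.1 is still 2% of the abandoned 1,900 target, so at the expected 400-480 participants it needs 39 users (8.1-9.75%) to fire

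*SAP*

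**What the plan says.** SAP 6.1 (Adverse Events) deals with concomitant UGT inducers in two steps.

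- The number of users during double-blind treatment "will be summarized combined across both study intervention groups".
- A second step is conditional: "If the number of such participants is >2% of the total 1,900 targeted for enrollment in this study", then "the users and non-users of UGT inducers will be summarized by each study intervention group as well and examined further", as necessary, for a relationship to key outcomes such as the patient-reported endpoints and the clinical outcomes in claims.

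SAP 1.4 (Sample Size Justification) says the 1,900 target is not expected to be met "by the scheduled end of study enrollment window in the first quarter of 2021" and that "the final anticipated enrollment may only be in the range of about 400-480 participants".

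SAP 1 (Introduction) dates the last version: "A final version of this SAP with editorial changes is posted on 1 July 2021". The summary of changes of December 30, 2020 lists a revision to Section 1.4 but none to Section 6.1.

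On the population for safety output, SAP 6 states: "Summaries of safety data will be based on the safety analysis set and will use claims data". SAP 2.3.4 defines that set: "The safety analysis set includes all randomized participants who received at least 1 dose of study intervention".

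**The concern.** Two current sections of the same SAP work from different trial sizes. Section 1.4 was rewritten for the enrollment shortfall, and the trigger in Section 6.1 was not. A percentage threshold normally describes a share of the participants studied. Here it is a share of a number the SAP itself says will not be reached, so the trigger becomes about four to five times as demanding as its stated 2%, and the text gives no reason for that.

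What is at stake is whether a pre-specified look by randomized group takes place. The SAP treats use above 2% as reason enough to compare users with non-users within each group and, where needed, to look for a relationship to key outcomes. With the old denominator, use clearly above 2% could pass without that look. Any by-group comparison would then be a later, discretionary decision. No endpoint, analysis set or type I error control is involved.

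**Working it through.** **Inputs**

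- Trigger: more than 2% of 1,900 (SAP 6.1).
- Expected enrollment: N = 400 to 480 (SAP 1.4).
- True UGT-inducer use: not given in either document, so assumed over a range of 1% to 8%.

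**The trigger as a count**

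0.02 × 1,900 = 38. The SAP does not print this count. The rule is strictly greater than, so it fires at 39 or more users.

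**That count as a share of the expected trial**

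- Share to be exceeded: 38/480 = 7.9%; 38/400 = 9.5%.
- First qualifying count: 39/480 = 8.1%; 39/400 = 9.75%.

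**Two percent of the expected trial**

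- 0.02 × 400 = 8.0, so the rule would fire at 9 users.
- 0.02 × 480 = 9.6, so it would fire at 10 users.
- If 5-10% of randomized participants were never dosed (an assumption), the safety analysis set would hold 0.90 × 400 = 360 to 0.95 × 480 = 456. Two percent is then 7.2 to 9.1, and the rule would fire at 8 to 10 users.

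**Chance that the rule fires**

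Let X be the number of users, binomial with size N and probability p. The table gives P(X > 38) for the rule as written and P(X > 0.02N) for 2% of actual participants. Paired figures are for N = 400 and N = 480.

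| Assumed use p | Expected users | As written | 2% of actual N | Original N = 1,900 |
|---|---|---|---|---|
| 1% | 4 / 4.8 | <0.01% / <0.01% | 2.1% / 2.4% | <0.01% |
| 1.5% | 6 / 7.2 | <0.01% / <0.01% | 15% / 19% | 3.4% |
| 3% | 12 / 14.4 | <0.01% / <0.01% | 85% / 91% | 99.6% |
| 5% | 20 / 24 | 0.007% / 0.23% | 99.8% / >99.9% | >99.9% |
| 8% | 32 / 38.4 | 12% / 48% | not needed | not needed |

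Solving P(X > 38) = 0.5 for p gives 9.7% at N = 400 and 8.1% at N = 480. Use has to be about that high before the written rule is as likely to fire as not.

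**Timing**

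The enrollment window was due to close in the first quarter of 2021 and the final SAP is dated 1 July 2021. The denominator could have been tied to actual participants in that version.

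**The case against.** The strongest reply has four parts.

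- *The text is explicit.* It names 1,900, so nobody can misapply it, and SAP 1.2 still gives about 1,900 as the planned number. This is correct: the rule can be carried out. The point that remains is that its 2% no longer describes the participants in the trial.
- *About 38 users may be a sensible floor.* With 9 or 10 users, roughly 5 per group, a by-group table is only descriptive and says little about outcomes. This has force, but the SAP states a percentage, not a minimum count, and gives no such reason. If a floor was meant, it should be written as one.
- *UGT-inducer use can be described elsewhere.* SAP 4.6 lists UGT inducers among the concomitant-medication classes, and nothing in 6.1 forbids a by-group table below the trigger. But 4.6 says only that medications may be grouped this way and promises no by-group summary.
- *The safety analysis set is not the only possible denominator.* The outcome check concerns endpoints analyzed in the full analysis set, and SAP Appendix 4 has no row for concomitant medication. This is fair: the safety set is a reasoned choice, not one the text compels. It fits because the rule sits in the safety section, which already uses that set.

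The limited consequence also stands. The combined count is reported regardless and the outcome check is discretionary.

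**Conclusion.** The concern holds, at low severity. The threshold was not updated when SAP 1.4 was revised. It requires at least 39 users where 2% of the expected enrollment would require 9 or 10. At an assumed 3-5% use, above the plan's own level, the by-group summary would almost never be triggered (probability at most about 0.2%), whereas in a trial of 1,900 it almost certainly would have been.

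The counts and shares rest only on the SAP's figures. The probabilities also assume a level of use and independent participants, and they take 400-480 as the number counted. A smaller safety analysis set would raise the share needed further. The practical loss is one descriptive table and a conditional outcome check.

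**What to change.** In SAP 6.1, replace the denominator of 1,900 targeted participants so that the condition reads: more than 2% of participants in the safety analysis set. If a minimum of 39 users was intended so that the by-group summary would be informative, state it as a count and give that reason.

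The cost is wording only, with no extra participants or data. A 2% rule is noisier at this size: at 1% true use it would fire with probability 2.1-2.4% (below 0.01% at 1,900), and at 1.5% with probability 15-19% (3.4% at 1,900). A false trigger costs one extra descriptive table. The SAP should say that with 9 or 10 users the by-group summary is descriptive only.

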6.2. Clinical Laboratory Tests

Not Applicable.

6.3. Vital Signs and Physical Examination Findings

Not Applicable.

6.4. Electrocardiogram

Not Applicable.

6.5. Other Safety Parameters

Not Applicable.

7. PHARMACOKINETICS/PHARMACODYNAMICS

Not Applicable.

8. BIOMARKERS

Not Applicable.

9. HEALTH ECONOMICS

As treatment of participants with symptomatic HF with JNJ-28431754 (canagliflozin) versus placebo may result in lower utilization of hospitalization/readmissions due to HF or other reason, ED visits, the duration of stay at each hospitalization/readmission, and discharge destination will be summarized by each intervention group. Comparison will be made between groups by analyzing differences in hospitalizations/readmissions and ED visits using the Fisher exact test. Descriptive statistics (eg, mean, median, minimum, and maximum) will be provided for the total length of stay in hospitals for each intervention group. Cumulative distribution function of the time to first occurrence of hospitalization/readmission will be estimated by the Kaplan-Meier method and tested using a log-rank test, stratified by the type of HF ejection fraction (ie, HFrEF or HFpEF). In addition, a Cox proportional hazards model with intervention and stratification factor as covariates will be fitted. A point-estimate along with 2-sided 95% CI for HR of the intervention effect (in terms of relative risk reduction (RRR) = $100 \times [1 - \text{HR}] \%$) will be provided. The cumulative event rate derived from Kaplan-Meier estimate will also be displayed graphically to evaluate the timing of event occurrence and the consistency of the treatment effect over time.

REFERENCES

1. Berglund P and Heeringa S. Multiple Imputation of Missing Data Using SAS®. 2014. Cary, NC: SAS Institute Inc. CDISC. “Analysis Data.
4. International Council For Harmonisation (ICH) of Technical Requirement for Pharmaceuticals for Human Use (final version, 2019): ICH Harmonised Guideline – Addendum on estimands and sensitivity analysis in clinical trials (to the guideline on Statistical Principles for Clinical Trials) - E9 (R1).

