8.2.4. Healthcare Resource Utilization and Health Economics

Healthcare Resource Utilization (HRU) and health economics data associated with medical encounters will be collected for all participants during the study. Protocol-mandated procedures, tests, and encounters are excluded. The data collected may be used to conduct exploratory economic analyses and will include:

- number and duration of first hospitalizations/readmissions (overall inpatient visit length of stay) for HF or any other reason
- number and duration of first hospitalizations/readmissions (overall inpatient visit length of stay) for any other events
- number of emergency room visits
- discharge destination

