1.2. Study Design

OVERALL DESIGN

This is a randomized, double-blind, placebo-controlled, decentralized, virtual, superiority study conducted in the US in participants with symptomatic HF (stratified by heart failure with HFrEF or HFpEF). This study examines the improvement in the KCCQ-TSS after 12 weeks of treatment with canagliflozin 100 mg or placebo. The study will continue for an additional 6 months without further study intervention to collect participant follow-up data from the smartphone, Fitbit, and claims in a real-world setting. At the end of the 12-week, double-blind treatment period, participants will be informed about their actual treatment allocation, whether they had been randomized to canagliflozin or placebo.

The study will enroll participants from large integrated health networks (IHNs) and physician practices in the US with the participants conducting many of their study-related activities through an app on a smartphone and will provide daily activity data recorded by using a Fitbit device. There will be no in-person clinic visits required by the study (see [Appendix 3: Schedule of Activities](#)).

[figure not shown]
The study consists of a screening period, a 12-week double-blind treatment period, and a 6-month follow-up (no intervention) observational period for each participant. Approximately 1,900 participants are planned for randomization into the study in a 1:1 ratio to canagliflozin 100 mg daily or placebo groups (950 in each study intervention group). After Week 12 (i.e., the end of the double-blind treatment period), the study will continue for an additional 6 months when study intervention will no longer be provided. Randomization will be performed using the interactive web response system (IxR). Participants will be stratified based on HF ejection fraction (EF) type – HFrEF or HFpEF.

Data collection from the smartphone, Fitbit device, and claims will continue until Month 9 for all endpoints. Specifically, study assessments include the following: KCCQ, PGIC, PGI-S, and an

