5.1.1. Level of Significance

A 5% level of significance will be used for all analyses. All statistical tests and 95% confidence intervals presented in the analyses of endpoints will be 2-sided.

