Baseline for daily step count and daily floors climbed variables will be defined by averaging the daily values over a 14-day interval starting with the first dose date. These data will be organized into a vertical file format to read one record per participant for averages over each 2-week interval during the entire study (including the EOT/EOS values, as applicable).

Claims Data – AEs, HRUs, Clinical Outcomes

Claims data pertaining to AEs of interest (as defined in the protocol), number of prescription fills, HRUs, and clinical outcomes reported with appropriate ICD codes applied at the individual participant level will be organized with one record for each incident (ie, hospitalization, etc.) date. Adverse events of interest include all severe hypoglycemic events, acute kidney injury, fractures, diabetic ketoacidosis, and lower limb amputation.

In addition, the following adverse events will be examined: hypotension; Fournier’s gangrene; genital mycotic infections; urinary tract infections (including urosepsis and pyelonephritis); increased urination; and hypersensitivity reactions including angioedema and anaphylaxis.

Self-reported AE data – Data from participants self-reporting adverse events (AEs) to a Call Center (set up by Care Innovations) will be manually submitted directly to the Sponsor (i.e. Janssen Safety [GMS]) for appropriate evaluation and analysis. Janssen Safety (GMS) will extract participant-reported AEs and transfer data to PRA for upload into the CCDS. Self-reported events will be captured from the date of the first dose of study intervention through the end of treatment (Month 3) plus 30 days. A listing of these self-reported AE may be produced based on available data.

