5.4. Exploratory Variables

5.4.1. Definition

The exploratory endpoints are the following:

-
- mean PGIC scores over time
 - changes in PGI-S scores from baseline to Week 12
 - change in HRU and health economics data
 - number of outpatient intravenous therapies, ED visits, and hospitalizations
 - time to first hospitalization/readmission for heart failure
 - time to first hospitalization/readmission for other events
 - time to death

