- Using data from the claims and data on deaths, time to first hospitalization/readmission for heart failure, time to first hospitalization/readmission for other events, and time to death will each be analyzed using a Cox's regression model both for the double-blind treatment period and the entire study duration and include terms for study intervention and stratification factor (HFrEF/HFpEF). Hazard ratios, corresponding 95% CIs, and associated p-values will be presented. Distribution of the times to first hospitalization/readmission for HF, time to first hospitalization/readmission for other events, and time to death will be displayed with Kaplan-Meier curves. Participants who do not experience any such events of interest during the study analysis period will be considered 'censored' in these analyses.

No adjustment for multiplicity will be performed for the exploratory analyses listed above.

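### The SAP's Fisher exact test on hospitalizations/readmissions and ED visits has no stated unit; on its natural reading it is valid but discards repeat events, and for ED visits it is the only between-group test

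*SAP*

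**What the plan says.** SAP section 9 (Health Economics) starts from the expectation that canagliflozin may reduce use of hospital and ED services, and plans a between-group comparison by "analyzing differences in hospitalizations/readmissions and ED visits using the Fisher exact test". It does not state the unit of analysis, a stratification or an allowance for follow-up time.

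The endpoints are defined as counts. SAP 5.4.1 lists the "number of outpatient intravenous therapies, ED visits, and hospitalizations". Protocol 8.2.4 lists the "number of emergency room visits" and the "number and duration of first hospitalizations/readmissions (overall inpatient visit length of stay) for HF or any other reason". Under SAP 5.1.2 the claims data "will be organized with one record for each incident (ie, hospitalization, etc.) date", so repeat events are available.

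Other analyses of the same data:

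- SAP 9 adds Kaplan-Meier curves, an EF-stratified log-rank test and a Cox model with the stratification factor, for time to first hospitalization/readmission.
- SAP 5.4.2 adds Cox models with the stratification factor for first heart failure hospitalization, first other hospitalization and death. It summarizes the event numbers descriptively.
- Protocol 9.4.4 calls for descriptive summaries of resource use, while Protocol 9.4.2.2 speaks of tabulation and comparison.

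On significance, SAP 5.1.1 says "A 5% level of significance will be used for all analyses", with two-sided tests. SAP 5.4.2 says "No adjustment for multiplicity will be performed for the exploratory analyses listed above".

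**The concern.** A Fisher exact test needs a 2x2 table of independent units, each with or without an event. A count of admissions that includes readmissions does not fit such a table unless it is first reduced to whether a participant had any event. That reduction gives a valid test, but a participant admitted four times then counts the same as one admitted once. Repeat use, which is part of what a utilization endpoint measures, does not enter the comparison.

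For hospitalization, the time-to-first-event analyses supply stratum and follow-up time, but they too stop at the first event. For ED visits there is no time-to-event or rate analysis, so the unstratified Fisher test stands alone. No between-group inference in either document uses repeat events. What is at stake is the power and relevance of an exploratory utilization comparison.

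**Working it through.** **The plan's own figure.** The documents give no power or event rate for this comparison. The SAP's approximately 95% power belongs to the primary endpoint. It reproduces (950 per arm, difference 3, SD 18: 95.3%) but has no bearing here.

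**Inputs.** Allocation is 1:1 (SAP 1.2). Anticipated enrolment is 400 to 480 (SAP 1.4), and the midpoint 440 gives 220 per arm. Tests are two-sided at 5% (SAP 5.1.1). Assumed, because the documents are silent: mean m = 0.2 or 0.4 events per participant, negative binomial dispersion k = 0 (Poisson), 1, 2 or 4, and rate ratio 0.7.

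**Step 1: events not used at participant level.** P(at least one event) = 1 − (1 + km)^(−1/k), or 1 − e^(−m) when k = 0. With 220 in an arm:

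- m = 0.2, k = 0: 44 events; 220 × 0.181 = 39.9 participants with an event; 9% of events unused.
- m = 0.4, k = 2: 88 events; 220 × 0.255 = 56.0 participants; 36% unused.
- m = 0.4, k = 4: 88 events; 220 × 0.2125 = 46.7 participants; 47% unused.

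**Step 2: power by hand for one setting (m = 0.4, k = 2).**

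- Rate comparison: the variance of the log rate ratio is the sum over arms of 1/(n × mean) + k/n. This is (1/88 + 2/220) + (1/61.6 + 2/220) = 0.0458, so SE = 0.214. Then z = 0.357/0.214 = 1.67 and power = Φ(1.67 − 1.96) ≈ 38%.
- Participants: proportions 0.255 and 1 − (1.56)^(−1/2) = 0.199, pooled 0.227. SE = √(2 × 0.227 × 0.773/220) = 0.0399, z = 1.38 and power ≈ 28% for an uncorrected test of proportions.

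The simulation below gives 39.8% and, with Fisher's conservatism, 25.5%.

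**Step 3: simulation.** 4,000 null and 3,000 alternative trials per setting. The rate comparison is a log rate-ratio test with empirical between-participant variance, standing in for a negative binomial model.

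| 220 per arm | Type I error, Fisher on participants | Type I error, rate | Power, Fisher on participants | Power, rate |
|---|---|---|---|---|
| m 0.2, k 0 | 3.2% | 4.8% | 24.9% | 31.3% |
| m 0.2, k 1 | 4.1% | 5.4% | 21.3% | 29.0% |
| m 0.2, k 2 | 3.9% | 5.1% | 17.9% | 26.3% |
| m 0.2, k 4 | 3.6% | 4.9% | 14.4% | 22.4% |
| m 0.4, k 0 | 4.0% | 5.3% | 47.6% | 59.1% |
| m 0.4, k 1 | 4.1% | 5.5% | 32.7% | 47.5% |
| m 0.4, k 2 | 3.7% | 5.1% | 25.5% | 39.8% |
| m 0.4, k 4 | 4.1% | 4.9% | 15.4% | 29.6% |

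At the originally planned 950 per arm, power is 53 to 98% for Fisher on participants against 69 to 99.5%, in the same direction throughout. Part of the gap is Fisher's conservatism rather than lost repeat events. At m = 0.2 and k = 0, the Step 2 formulas give 31% against 33%.

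**Step 4: if the test were run on events over participants.** Such a table assumes variance m(1 − m) per participant, while the actual variance is m(1 + km). The ratio at m = 0.4, k = 2 is 1.8/0.6 = 3, so the nominal 5% becomes about 2 × [1 − Φ(1.96/√3)] ≈ 26% (simulated 23.4%). Across the settings at 220 per arm, the simulated rate is 6.1 to 30.5%.

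**Not sized.** The simulation used equal follow-up and no EF strata, so the loss from ignoring these for ED visits has no figure here.

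**The case against.** The strongest case for the plan is that its ordinary reading is sound. A Fisher test presupposes a table of participants. SAP 5.1 summarizes categorical data as participant counts and percentages, SAP 6.1 does the same for adverse events, and the only other Fisher test (SAP 5.4.2, activity level against baseline characteristics) is also per participant. The one-record-per-incident rule describes file layout, not the unit of analysis. Protocol 8.2.4 attaches the word first to its hospitalization counts, which brings them closer to participants with an event. All of this stands.

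A reader might infer that the SAP inflates type I error. The documents do not support that: it needs an event-level table that they nowhere prescribe, and that cannot be built once events outnumber participants. The 6 to 31% range shows only why the unit should be written down.

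A reader might also infer that stratum and follow-up time are ignored throughout. That holds only for ED visits, because SAP 9 and 5.4.2 cover first hospitalization with log-rank and Cox analyses.

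It is also fair that the comparison is exploratory, has no multiplicity control, supplements descriptive summaries and is underpowered by either method in most settings at 220 per arm. Preferring a rate model is then largely a preference for power and for matching the endpoint.

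Three things remain: the unit is unstated, no between-group inference uses repeat events, and ED visits have no second analysis.

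**Conclusion.** The point holds as a low-severity, cheap improvement. The Fisher test on participants is valid (simulated type I error 3.2 to 4.1% at 220 per arm), but it answers whether a participant had any event, while the endpoints are numbers of events. Under the assumed rates it had less power than the rate comparison in every setting: about 14 to 48% against 22 to 59%, with type I error of 4.8 to 5.5% for the latter. The size depends on event rates, dispersion and a rate ratio that the documents do not give. That repeat events are dropped follows from the participant-level reading itself. The primary and first key secondary conclusions are unaffected.

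**What to change.** In SAP section 9:

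1. State the unit of analysis and the analysis period for each comparison.
2. Compare the numbers of hospitalizations/readmissions and of ED visits by negative binomial regression, with treatment and EF stratum as terms and log follow-up time as offset. Report the rate ratio and 95% CI. Name a Poisson model with robust variance as the fallback if events are sparse or the model does not converge.
3. Keep any test of proportions strictly for participants with at least one event, and stratify it by EF type (Cochran-Mantel-Haenszel).

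The cost is SAP wording and one more standard model on data already extracted. The downside is possible non-convergence with few events, which the fallback addresses. No new data are needed.
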